Population:	Patients seen in the emergency department who meet criteria for DVA and study eligibility will be approached for enrollment by research staff. Inclusion criteria include: Expected inpatient admission for 72 hours or more, Age 18 or older, able to provide consent, English speaking, expected inpatient admission, two staff have looked for IV access or patient has history of requiring ultrasound guided IV. Exclusions: Prisoner, not suspected of having bacteremia, No phone number for follow up, Pregnancy, known to require long term IVA with a CVC or MC, no target vessel <1.6cm in depth, or do not have an upper extremity (left or right arm) that can accept a deep venous IV (example dialysis fistula in one arm and upper extremity deep venous thrombosis in the contralateral arm). Minimum sample size of 108, 54 in each study arm to be appropriately powered for this clinical question. It is likely we will need to enroll more than 108 after exclusions and randomization to ensure we obtain 54 in each arm.
Intervention:	Patients will be randomized to receive a standard UGPIV that is 4.88cm in length or a 10cm midline catheter.
Objectives:	
Aim 1: To determine if UGPIVs have a higher failure rate than midline catheters within 72 hours of placement.
 
Aim 2: To perform a direct cost analysis of UGPIV against that of the midline catheter over the length of the hospitalization.
 
Aim 3: To determine experience and satisfaction with each device to determine patient preference.

Design/Methodology:	A convenience sample of patients will be randomized to one of two arms. The first arm will receive standard UGPIV. The second arm will receive a MC. Patients will be randomized based on pre-randomized patient enrollment packets. Patients will receive one of two venous access options either the UGPIV or the MC in the ED. Catheter survival will be assessed based on time to when a failed catheter is found to be dysfunctional or when a catheter is removed

	by hospital staff. Study personnel will review medical records and visit patients daily Monday to Friday to assess how the IV is working. They will check to make sure that catheters have not been removed and have not malfunctioned by speaking with the patient or hospital staff.
Total Study Duration:	Expected April 1, 2018 to June 30 th , 2019

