4.1.1 Primary Outcome Measures

The primary outcome measure is survival of each venous access device. Time of device placement will be stamped based on placement of the IV at the time of the procedure on the ultrasound machine. Research assistants will daily visit patients Monday to Friday to determine if the IV are still in place and review medical records for overnights and weekends. As a part of hospital policy vascular access sites are flushed regularly to assess for failures and complications. Any removal of IVs should be documented in nursing notes. We will review these notes; however, we will also visit patients daily during the week to determine if the UGPIV or MC is still in place. If the device is removed the patient and the treating nurse will be asked to identify the cause of the failure (removal for patient preference, thrombosis, infiltration, completion of clinical care and no longer needed, etc). Data will be entered into REDCap. Data will also be written down by the physician placing the UGPIV as well as the MC. See attached. These will be REDcap forms that are printed and then later filled into the database to allow for physician ease. Time of device failure will be documented in REDCap when determined. It is possible that patients will be discharged with the device in place. If this is the case, we will review the medical record to determine when the device is expected to be removed and call the patient to determine when the device failed or was removed. It is however likely the patient will get all care delivered through BMC and we will know when the device fails or is removed due to returning for clinical care.

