The only study visit will be the ED visit and hospitalization associated with this visit. Patient contact information including phone number and address will be obtained. The length of the study may last up to 1 month in duration.

All patients who are determined to have DVA and require UGPIV have the "procedure resident" paged to perform the study. The procedure resident will be notified when study personnel are available to consent and perform the study measures. Patients will be approached by RAs or study staff to obtain consent. They will ask the nurse if at least two staff attempted to place IV access. If the patient is a known DVA patient and cannot receive standard IV access due to known history (such as sickle cell disease, or dialysis) two staff do not need to attempt IV access. Patient must be able to consent and be

have a high likelihood of expected admission based on physician evaluation. The total study duration will last as long as the patient has an MC or PGIV in place and are hospitalized up to 29 days.

The patient will be consented by RAs or study staff physicians. Patients will be randomized based on packet assignment. Packets will contain a preassigned randomized piece of paper which will determine which device will be used. Patients may withdraw themselves from the study at any time as is already the case for clinical care by requesting their MC or UGPIV to be removed. They may also ask our staff to remove themselves from the study. Once the device is placed per hospital recommendations, the physician who placed the line will administer a brief survey to the patient regarding pain and preferences.

Research assistants will daily during the week visit patients to determine if IVs placed in the ED are still in place. Because they are RAs they will not access the failure of these devices and will require the clinical team to make these assessments based on hospital policies for daily assessments. If the patient is discharged with the midline in place, the research assistant will attempt to reach the patient by phone to determine if there are device failures or complications. They will document these within the daily assessment form used for inpatients.

10 Assessment of Safety and Data Safety Monitoring Plan (DSMP)

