12.3 Statistical Methods

Statistical analysis and study measures

Catheter survival will be determined by how long an IV lasts prior to being removed measured in hours. We will include failures if a patient accidentally pulled out their access, thrombosis, infiltration or site bleeding, infection leading to removal, or there is too much pain reported resulting in removal. If it is known that a patient intentionally removes the IV or midline it will not be documented as a failure. We will report data based on a Kaplan Meir curve to

display catheter survival. We will use a t-test of means to compare failure rates between the two groups.

Direct Cost Analysis

A complete cost effectiveness analysis is beyond the scope of this proposal. We therefore wish to capture the direct costs and easily estimated costs associated with this change in practice.

We expect use of the midline catheter will be a cost effective change in practice.

Although more upfront costs, we expect that because the midline can dwell up to 29 days and is associated with fewer failures, it will be less expensive in the long run. We will obtain information from EPIC, as to whether a UGPIV or Midline fails. Nursing staff at BMC are required to file daily notes that include IV access type and location and daily events. We will have our study staff follow-up with patients or their medical teams to determine survival of the IV line if it cannot be determined from the medical record. If a failure occurs we will document the date and type of failure, i.e. thrombosis, infiltration, etc. We will then capture each additional IV that is placed and the associated billing from that procedure.

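### The event for the primary endpoint is defined inconsistently across the Synopsis and Sections 4.1.1, 9 and 12.3, and elective removals before 72 hours have no stated handling

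*Combined protocol and SAP*

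**What the plan says.** Four places bear on what ends catheter survival and what counts as a failure.

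- **Synopsis, Design/Methodology.** Survival is assessed by "time to when a failed catheter is found to be dysfunctional or when a catheter is removed" by hospital staff. No reason for removal is required.
- **Section 4.1.1.** Once a device is out, the patient and nurse are asked to "identify the cause of the failure (removal for patient preference, thrombosis, infiltration, completion of clinical care and no longer needed, etc". Preference and completed care therefore appear as kinds of failure.
- **Section 9.** Patients may withdraw from the study "by requesting their MC or UGPIV to be removed"; the next sentence adds that they may also ask staff to take them out of the study.
- **Section 12.3.** It opens with "Catheter survival will be determined by how long an IV lasts prior to being removed measured in hours", again without a reason. It then lists failures: accidental pull-out, thrombosis, infiltration or site bleeding, "infection leading to removal, or there is too much pain reported resulting in removal". Completed care is not listed. The next sentence is "If it is known that a patient intentionally removes the IV or midline it will not be documented as a failure".

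Section 12.3 uses a Kaplan-Meier curve for display and a t-test to compare failure rates. No section says whether a line removed for a reason other than failure is censored, excluded or counted as a survivor, or which section governs.

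**The concern.** This is the event definition of the primary endpoint. The stated comparison is between failure rates, so each line that moves from one category to another moves the result directly. The treating nurse and the patient supply the cause of removal; the devices are visibly different and no blinding is described, so a loose definition leaves room for classification that depends on the arm. If the definition is settled only after outcomes are known, the choice is open to the charge of being data-driven.

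**Working it through.** **1. The passages side by side**

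| Removal | Synopsis | 4.1.1 | 9 | 12.3 |
|---|---|---|---|---|
| Staff remove the line for reported pain | Ends survival | Pain not named | Withdrawal route if the patient asked | Failure (listed) |
| Patient deliberately removes it because of pain | Not covered (staff removal only) | Nearest item is preference, under failure | Not addressed | Pain item says failure; next sentence says not |
| Staff remove it because care is complete | Ends survival | Named under failure | Silent | Ends survival; not on the failure list |
| Patient asks for removal, reason unrelated to the device | Ends survival if staff remove it | Preference, under failure | Withdrawal route | Ends survival; not on the list |

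The first row has an answer for classification, in 12.3. The other three do not. In any row with a patient request, follow-up afterwards is undefined.

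**2. The plan's own sample size**

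Inputs from Section 12.2: a 25-point difference, power 0.8, alpha 0.05, 54 per arm, UGPIV failure 40-44%. Assumed, because not stated: a two-sided test and the pair 44% vs 19%.

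n = [1.96·√(2p̄(1−p̄)) + 0.8416·√(p₁(1−p₁) + p₂(1−p₂))]² / d², with p̄ = 0.315 and d = 0.25. This gives just over 53.0, rounded up to 54 per arm, so the stated figure reproduces. (42% vs 17% gives 52; 40% vs 15% gives 49.)

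Power = Φ[(d − 1.96·SE₀)/SE₁], where SE₀ = √(p̄(1−p̄)(1/n₁+1/n₂)) and SE₁ = √(p₁(1−p₁)/n₁ + p₂(1−p₂)/n₂). At 54 per arm: Φ[(0.25 − 1.96×0.0894)/0.0861] = 80.7%.

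**3. Completed-care removals counted as failures**

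Assume a share r, equal in both arms, of lines that would not otherwise fail is removed by 72 hours because care is complete. The observed rate becomes p + (1−p)r. The documents give no value for r.

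| r | 44% vs 19% becomes | Power | 40% vs 5% becomes | Power |
|---|---|---|---|---|
| 0 | 44.0 vs 19.0 | 80.7% | 40.0 vs 5.0 | 99.6% |
| 10% | 49.6 vs 27.1 | 67.6% | 46.0 vs 14.5 | 95.6% |
| 20% | 55.2 vs 35.2 | 55.2% | 52.0 vs 24.0 | 86.1% |
| 30% | 60.8 vs 43.3 | 44.4% | 58.0 vs 33.5 | 73.0% |

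The pair 40% vs 5% is what the cost analysis in 12.3 anticipates.

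**4. Pain-driven UGPIV removals not counted as failures**

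Assume 3 or 5 such removals, in the UGPIV arm only, with 44% vs 19%.

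- Coded as non-failures, n stays 54: 0.44 − 3/54 = 38.4%, or 0.44 − 5/54 = 34.7%. The difference is 19.4 or 15.7 points; power 61% or 45%.
- Dropped as withdrawals, the denominator shrinks too: (23.76 − 3)/51 = 40.7%, or (23.76 − 5)/49 = 38.3%. The difference is 21.7 or 19.3 points; power 69% or 59%.
- At 40% vs 5%, coding 3 or 5 as non-failures leaves 98% or 95%.

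**The case against.** The strongest reply is that only 12.3 states an analysis rule. The bracket in 4.1.1 ends in an open-ended *etc* and reads as a pick-list of removal reasons under a loose heading. The Synopsis sets the end of observed time, which in a Kaplan-Meier analysis need not be an event. Section 9 describes a patient's right to stop and does not say that such patients leave follow-up or the analysis.

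Much of this is fair, and it rules out some stronger readings. A reader might infer that a patient who asks staff to take out a painful line is at once a failure, a non-failure and a withdrawal. The text does not support that: 12.3 counts removal for reported pain as a failure, and its exclusion concerns a patient who removes the line. Deliberate removal, preference and request are not the same act. Nor is completed care an endpoint event under 4.1.1 alone, since the Synopsis also ends survival at staff removal.

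The reply does not settle the point. No section says that 12.3 governs or that 4.1.1 is only a pick-list. Even within 12.3, the opening sentence and the failure list differ on completed care, and two neighbouring sentences collide when a patient deliberately removes a line because of pain.

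The power figures can also be challenged: the shares are assumed, recoding only UGPIV lines is one-sided, and the Synopsis requires an expected admission of 72 hours or more, which makes a large completed-care share less likely. That stands as a limit on size. It does not make the share zero: Section 5 describes screening for patients likely to need access for at least two hospital nights, which can end before 72 hours.

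**Conclusion.** The concern holds as an inconsistent event definition plus a missing rule for elective removals. Applying one stated rule rather than another changes the failure rates being compared, so this is more than missing detail. A t-test of failure rates can only count an electively removed line as a failure, count it as a success, or drop it. None of these is a valid treatment of a line whose 72-hour status was never observed.

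The size is uncertain. Under the assumed pair 44% vs 19%, power falls from 81% to between 68% and 44% across the completed-care shares tried, and to 61-45% or 69-59% for the pain recodings. At the plan's more optimistic 40% vs 5%, power is 73% or more in every case shown. A reader might infer that the trial is underpowered as planned. The documents do not establish that, because they give neither the removal shares nor the rate pair behind the 25-point difference. The textual conflict depends on none of these assumptions.

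**What to change.** Reconcile the Synopsis and Sections 4.1.1, 9 and 12.3 into one outcome-classification table, fixed before outcomes are examined.

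- In 4.1.1, record the reason for removal instead of the cause of failure.
- Count device-related removals as failures, including patient-initiated removal because of pain.
- Censor, at the time of removal, lines taken out because care is complete or on a request unrelated to the device.
- Replace the t-test with a 72-hour comparison that uses censored times, for example the difference in Kaplan-Meier 72-hour failure or a log-rank test. Censoring cannot feed the stated t-test, so this change must accompany the table.
- State in Section 9 that removal of the device does not by itself end follow-up or take the patient out of the analysis.

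This changes how outcomes are classified and analysed, not when a device is removed. The reason for removal is already collected, so the cost is protocol wording and one REDCap reason-for-removal field, with no extra patients or visits.

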4.1 Study Objectives

Aim 1: To determine if UGPIVs have a higher failure rate than midline catheters within 72 hours of placement.

There are several reasons why UGPIVs may fail. UGPIVs are shorter than midline catheters, and shorter catheters may fail due to infiltration which can be a result of malposition as well as having the catheter pull out of the vessel. We suspect that by using a midline catheter with a guidewire for placement with additional catheter length placed into the vessel, midlines will be superior to UGPIVs with regards to survival time of the catheter.

Hypothesis: Midline catheters have a lower failure rate at 72-hours compared to ultrasound guided peripheral IVs.

Aim 2: To perform a direct cost analysis of UGPIV against that of the midline catheter.

This study will not be large enough to complete a robust cost effectiveness analysis to compare UGPIV to midline catheters. As a part of this study we will collect information including but not limited to: the number of catheters used for IVA attempts, time for placement of each device, complications, and need for additional IV access during hospitalization (MC, PIV, or CVC).

Hypothesis: Midline catheters are a cost effective change in clinical practice due to lower complication rate and longer dwell times.

Aim 3: To determine patient experience and satisfaction with each device to determine patient preference.

Our goal will be to compare UGPIV to MC for patient experience (including pain, satisfaction, and preference) based on survey.

Hypothesis: Pain scores will be similar between the UGPIV and MC group, however patients will prefer the placement of the MC.

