4.1.2 Secondary Outcome Measures

Secondary outcomes will be determined based on review of the clinical record and patient responses to a questionnaire. All procedures that are performed including placing an IV and removing an IV should be available to determine additional costs associated with IV access during the hospitalization.

Responses for each of the questions on the study questionnaire will be compared between the study groups. Appropriate statistical tests will be used for bivariate, categorical, or continuous variables.

5 Study Design

This is a convenience sample, randomized controlled trial to determine if the midline catheter is superior to the ultrasound guided IV with respect to survival at 72 hours. Folders will be sealed and pre-randomized using computer number randomization. Patients will be screened for enrollment in the emergency department. Patients will be considered eligible for enrollment if they are considered a difficult vascular access patient and are expected to require hospitalization after physician assessment. We have selected patients who are felt to require admission as the midline catheter is indented for longer dwell times and are attempted to screen for patients who are likely to require IV access for a minimum of two hospital nights. There will be two arms 1) those randomized to standard care with ultrasound guided IV, and 2) those randomized to receive a midline catheter. Data will be collected from the medical record into redcap as well as an enrollment log stored on the hospital G drive. These will be password protected. Data will also be stored on QPATH which is a secure software for storing medical imaging (ultrasound images). Data lastly recorded on paper sheets including consent forms will be stored in locked filing cabinets with only study personnel access. Data will be collected directly from the patient as well as from the medical record.

6 Potential Risks and Benefits

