12.1 Study Hypotheses

The primary hypothesis is that midline catheters will be superior to ultrasound guided IVs with relation to survival time.

Secondary assessment will 1) attempt to prove that MC are superior to UGPIV with relation to cost effectiveness despite their overall higher upfront cost. 2) Patients will experience similar pain between MC and UGPIV, however will prefer the MC knowing the survival of the catheter is longer.

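### The primary endpoint is worded two ways, and its only test, a t-test of means, has no stated variable and no rule for working catheters removed when care ends; run on hours, it compares dwell time rather than failure

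*Combined protocol and SAP*

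**What the plan says.** The plan describes the primary question in two ways.

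- **Failure by 72 hours.** Aim 1 (synopsis and Section 4.1) carries the hypothesis "Midline catheters have a lower failure rate at 72-hours compared to ultrasound guided peripheral IVs". Section 5 sets out to show that the midline is "superior to the ultrasound guided IV with respect to survival at 72 hours".
- **Survival time.** Section 12.1 states that "midline catheters will be superior to ultrasound guided IVs with relation to survival time". Section 12.3 measures it this way: "Catheter survival will be determined by how long an IV lasts prior to being removed measured in hours". The synopsis, which also contains Aim 1, says "Catheter survival will be assessed based on time to when a failed catheter is found to be dysfunctional or when a catheter is removed", and goes on to name hospital staff as those removing it. Section 4.1.1 gives device survival with no time point.

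On what counts as failure, Section 12.3 says "We will include failures if a patient accidentally pulled out their access, thrombosis, infiltration or site bleeding, infection leading to removal", and adds removal for pain. Intentional removal by the patient is not a failure. End of care is not on the list. Section 4.1.1 nevertheless gives "completion of clinical care and no longer needed" as an example when staff are asked for the cause of a failure.

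On analysis, Section 12.3 uses a Kaplan-Meier curve for display, followed by one test: "We will use a t-test of means to compare failure rates between the two groups". No log-rank test, Cox model or censoring rule appears anywhere.

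**The concern.** The t-test can be run in two ways, and the plan does not choose between them.

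1. **On hours to removal**, which is how Section 12.3 defines survival. Every working catheter taken out at the end of care then counts as the end of survival, so the test compares dwell.
2. **On a 0/1 indicator of failure by 72 hours**, which suits the phrase about failure rates better. This is close to a chi-square test. A catheter electively removed at, say, 40 hours counts as a success, so the estimate is a cumulative incidence with elective removal as a competing event. A Kaplan-Meier curve that censors those removals shows something different.

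Two analysts following the plan could therefore run different primary tests and reach different conclusions. The hours reading is also sensitive to any difference between arms in when working catheters come out, and the documents conflict on that. Section 3.2 gives UGPIVs an intended use of up to 3 days, and the cost projection in Section 12.3 applies a 72-hour dwell limit. Section 6.1 sets no fixed limit and bases replacement on site assessment.

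**Working it through.** **1. What the sample size was built for.** Section 12.2 gives alpha 0.05, power 0.8 and a 25-point difference. It gives neither the pair of rates nor the sidedness. I assume a two-sided test and try 45% vs 20% and 44% vs 19%; the second pair uses the top of Section 12.2's 40-44% range. The pooled two-proportion formula is

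n = [1.96·√(2·p̄(1−p̄)) + 0.8416·√(p1(1−p1) + p2(1−p2))]² / (p1−p2)²

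- 45% vs 20%, p̄ = 0.325: (1.2982 + 0.5373)² / 0.0625 = 3.369 / 0.0625 = 53.9, so 54.
- 44% vs 19%: 53.0 (fractionally above 53), so 54.

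The stated 54 per arm is reproduced as a comparison of proportions. The plan gives no mean or SD of hours, so the hours reading has no sample-size basis.

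**2. How many catheters the missing rule touches.** The cost projection in Section 12.3 has 22 UGPIV and 3 midline failures. That leaves 54−22 = 32 and 54−3 = 51 ending without failure: 83 of 108, or 77%. On the hours reading, most values would be times to a non-failure removal.

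**3. Simulation set-up.** There are 54 per arm and 5,000 trials per scenario, so the Monte Carlo standard error is at most √(0.25/5000) = 0.7 points. Failure is exponential with rate −ln(1−f)/72, where f is 72-hour failure. The documents give no timing for elective removal, so it is an assumption shown as a range. Three shapes are used: exponential; Weibull with shape 2; and none before 48 hours with an exponential tail. The last two fit the synopsis criterion of expected admission of 72 hours or more better.

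**4. Power, true failure 45% vs 20%, same elective removal in both arms.**

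| Elective removal | Median (h) | t-test, hours | t-test, 0/1 | Log-rank to 72 h |
|---|---|---|---|---|
| Exponential | 48 / 72 / 120 | 26 / 41 / 64% | 57 / 65 / 70% | 61 / 68 / 73% |
| Weibull | 72 / 96 / 120 | 43 / 58 / 70% | 72 / 74 / 77% | 73 / 76 / 78% |
| None before 48 h | 72 / 96 / 120 | 54 / 66 / 74% | 75 / 79 / 80% | 76 / 79 / 81% |

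The hours test is 7 points (81−74) to 35 points (61−26) below log-rank. The 0/1 test is at most about 4 points below. With 72-hour status known for everyone, the 0/1 test has 80.5% power and log-rank 80.9%. Using 44% vs 19% moves these figures by about 3 points or less.

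**5. Rejection rate with failure equal at 40% in both arms.**

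- Hours test, same elective removal: 4.5 to 5.8%.
- Hours test, if working UGPIVs come out at 72 hours and midlines do not: 24 / 52 / 84% (exponential), 31 / 68 / 88% (Weibull), 31 / 76 / 91% (none before 48 h), at the same medians as in the table.
- Hours test, no limit, median elective removal 72 h for UGPIV and 96 h for midline: 12% (exponential), 30% (Weibull), about 33% (none before 48 h).
- In these scenarios log-rank and the 0/1 test stay near nominal, at about 5 to 6%.

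A separate simulation with gamma end-of-care times and 20% failure in both arms agrees. The hours test rejects in 4% at mean 96 h in both arms, 23% at 96 vs 120 h and 55% at 96 vs 144 h.

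**6. What the 0/1 reading reports.** With exponential elective removal, median 48 h, observed 72-hour failure is λf/(λf+λc)·[1−exp(−72(λf+λc))], where λc = ln2/48 = 0.01444.

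- UGPIV: λf = −ln(0.55)/72 = 0.00830, giving 0.365 × 0.806 = 29%.
- Midline: λf = −ln(0.80)/72 = 0.00310, giving 0.177 × 0.717 = 13%.

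So 45% vs 20% appears as 29% vs 13%. With none before 48 h and median 120 h it appears as 44% vs 19%.

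**The case against.** The strongest reply is that the quoted test concerns failure rates, Aim 1 and Section 5 fix the time at 72 hours, and 54 per arm is a two-proportion figure. The 0/1 reading is then the natural one, and it is sound. In the removal patterns that best fit the admission criterion it loses only 0 to 2 points to log-rank. At the 40% vs 5% failure projected in Section 12.3, it has 96 to 99.8% power in six removal scenarios, against 43 to 91% for the hours test. All of this stands. It does not settle the matter, because the same section defines survival in hours to removal and Section 12.1 makes survival time the primary hypothesis.

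It can also be said that the failure list leaves out end of care and that a Kaplan-Meier curve normally implies censoring. Both are fair inferences, but neither is written as a rule and a t-test cannot use censoring.

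The highest false-positive figures are conditional. If working UGPIVs stop at 72 hours, a median of 72 h implies 54 × 0.60 × 0.50 = 16 stopped at the limit. That is near the 18 in the cost projection and gives 31 to 52%. The 84 to 91% scenarios imply about 21 to 26. The lower range is closer to the plan's own numbers, and still far above 5%.

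Finally, log-rank needs failure times, which here come from weekday visits and chart review, and it may disagree with a risk difference at 72 hours. Both are real limits of the remedy.

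**Conclusion.** The concern holds, and it must be fixed before analysis. The two endpoint wordings, the unnamed test variable and the missing rule for working catheters are plain from the text and need no simulation. Only one of the two permitted readings answers the 72-hour question the trial was sized for. The other costs 7 to 35 points of power relative to log-rank, and it can show a midline advantage with equal failure hazards if working UGPIVs are removed earlier. These sizes rest on exponential failure, independent elective removal with assumed timing, and an inferred pair of rates. The sample size is not in error: 54 per arm is right for two proportions with complete 72-hour observation.

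**What to change.** - Name one primary endpoint in Sections 4.1.1, 12.1 and 12.3: device failure within 72 hours of placement, using the Section 12.3 failure list.
- State that working catheters removed for non-failure reasons (end of care, intentional patient removal, death) are censored at removal. Devices still in place at discharge in patients who cannot be reached are censored at last known status.
- Replace the t-test with a log-rank test truncated at 72 hours. Report Kaplan-Meier 72-hour failure by arm, with the risk difference and 95% CI.
- Add a cumulative-incidence sensitivity analysis with elective removal as a competing event, because censoring assumes that removal is uninformative.
- Reword Section 4.1.1 so that completion of care is a reason for removal, not a cause of failure. Keep survival to 29 days as secondary.
- Reconcile Sections 3.2, 6.1 and the Section 12.3 cost projection on UGPIV dwell.
- State that 80% power assumes complete 72-hour observation.

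The cost is wording; removal times and reasons are already collected. The downside is that early elective removal lowers power under any test. Restoring 80% by log-rank at 45% vs 20% would take about 57 per arm (none before 48 h, median 72 h), 65 (exponential, 120 h), 73 (exponential, 72 h) or 84 (exponential, 48 h). The sponsor can enlarge the trial or accept the lower power, and the plan should say which.
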